3.3.4 PRO-CTCAE

The PRO-CTCAE is included to address tolerability from the patient's perspective. It was developed by the National Cancer Institute (NCI). The PRO-CTCAE will only be administered in English, German, Spanish and Japanese. In countries where a linguistically validated version does not exist, the English version is administered for patients who signed English informed consent. The PRO-CTCAE was developed in recognition that collecting treatment-related symptom data directly from patients using PRO tools can improve the accuracy and efficiency of symptomatic AE data collection. This was based on findings from multiple studies demonstrating that physicians and nurses underestimate treatment-related symptom onset, frequency, and severity in comparison with patient ratings (Basch et al 2009, Litwin et al 1998, Sprangers and Aaronson 1992). These treatment-related symptoms have been converted to patient terms (e.g. the CTCAE term "myalgia" has been converted to "aching muscles"). For several symptoms, like fatigue and pain, additional questions are asked about the frequency, severity, and interference with usual activities. The items included in the PRO-CTCAE have undergone extensive qualitative review among experts and patients. These items have been extensively evaluated by cancer subjects to be clear, comprehendible, and measure the symptom of interest. For this study, 9 symptoms are considered relevant for this cancer treatment: swallowing, nausea, heartburn, diarrhea, wheezing, rash, itchy skin, skin burns from radiation and headache (see CSP Appendix H).

3.3.5 PRO compliance rates

Summary measures of overall compliance and compliance over time will be derived for the EORTC QLQ-C30, LC13 and EQ-5D-5L respectively. These will be based upon:

- Received questionnaire = a questionnaire that has been received and has a completion date and at least one individual item completed.
- Expected questionnaire = a questionnaire that is expected to be completed at a scheduled assessment time e.g. a questionnaire from a patient who has not withdrawn from the study at the scheduled assessment time but excluding patients in countries with no available translation. Date of study discontinuation, PFS2 or death will be mapped to the nearest visit date to define the number of expected forms.
- Evaluable questionnaire = a questionnaire with a completion date and at least one subscale that is non-missing.
- Overall PRO compliance rate is defined as: Total number of evaluable questionnaires across all time points, divided by total number of questionnaires expected to be received across all time points multiplied by 100.
- Overall patient compliance rate is defined for each randomized treatment group as: Total number of patients with an evaluable baseline and at least one evaluable follow-up questionnaire (as defined above), divided by the total number of patients expected to have completed at least a baseline questionnaire multiplied by 100.

Compliance over time will be calculated separately for each visit, including baseline, as the number of patients with an evaluable questionnaire at the time point (as defined above), divided by number of patients still expected to complete questionnaires. Similarly, the evaluability rate over time will be calculated separately for each visit, including baseline, as the number of evaluable questionnaires (per definition above), divided by the number of received questionnaires.

3.4 Safety

Safety and tolerability will be assessed in terms of adverse events (AEs) (including serious adverse events [SAEs]), deaths, laboratory data, vital signs, electrocardiograms (ECGs) and exposure. These will be collected for all patients.

'On treatment' will be defined as assessments between date of the first dose and 90 days following last dose of the study treatment or up to and including the date of initiation of the first subsequent anticancer therapy (excluding radiotherapy) (whichever occurs first).

The safety analysis set will be used for reporting of safety data.

3.4.1 Adverse events (AEs)

AEs and SAEs will be collected throughout the study, from the date of informed consent until 90 days after the last dose of the study treatment. The Medical Dictionary for Regulatory Activities (MedDRA) (using the latest or current MedDRA version) will be used to code the AEs. AEs will be graded according to the National Cancer Institute Common Terminology Criteria for AEs (CTCAE Version 4.03). A treatment emergent adverse event (TEAE) is an AE with an onset date/time or a pre-existing AE worsening (taking the last grade prior to dosing as the reference) on or following the first dose of study treatment through to 90 days after the last dose of the study treatment or initiation of first subsequent therapy (whichever occurs first). All AEs will be listed however only TEAEs will be summarized. For each treatment group, in the unlikely event of the two components being administered separately then date of first dose/last dose will be considered as the earliest/latest dosing date of either component.

Adverse events that have missing causality (after data querying) will be assumed to be related to study drug ("durvalumab or placebo" or "tremelimumab or placebo"), with the exception of causality assessments that are not applicable for the patient, e.g. causal relation to durvalumab for patients in the placebo arm.

AEs of special interest (AESI) and AEs of potential interest (AEPI)

Some clinical concepts (including some selected individual preferred terms [PTs] and higher level terms [HLTs]) have been considered "AEs of special interest" (AESI) to the durvalumab program. AESIs represent pre-specified risks which are of importance to a clinical development program.

The AESIs reported in the AstraZeneca-sponsored durvalumab studies are defined as AEs with a likely inflammatory or immune-mediated pathophysiological basis resulting from the mechanism of action of durvalumab and requiring more frequent monitoring and/or interventions such as systemic corticosteroids, immunosuppressants, and/or endocrine therapy. Endocrine therapies include standard endocrine supplementation, as well as treatment of symptoms resulting from endocrine disorders (for example, therapies for hyperthyroidism include beta blockers [e.g. propranolol], calcium channel blockers [e.g. verapamil, diltiazem], methimazole, propylthiouracil, and sodium perchlorate).

The Adverse Events of Possible Interest (AEPIs) reported in the AstraZeneca-sponsored durvalumab studies are defined as AEs that could have a potential inflammatory or immune-mediated pathophysiological basis resulting from the mechanism of action of durvalumab but are more likely to have occurred due to other pathophysiological mechanisms, thus, the likelihood of the event being inflammatory or immune-mediated in nature is not high and/or is most often or usually explained by the other causes. These AESIs and AEPIs are identified as a list of categories provided by the clinical team. Other categories may be added as necessary or existing terms may be merged. A further review will take place prior to DBL to ensure any further terms not already included are captured within the categories.

Immune-mediated Adverse Events (imAE)

To fully characterize the AESI (excluding AESI group Infusion related/ Hypersensitivity/ Anaphylactic reactions) during which systemic corticosteroids, endocrine therapy, or other immunosuppressants were administered), the Sponsor will classify AESIs as immunemediated AEs (imAEs) or not imAEs. Further details are provided in an imAE Charter.

The imAEs will be determined by a programmatic algorithm that requires specific treatment for AESIs to be considered imAEs such as systemic corticosteroids, immunosuppressants, and/or endocrine therapy. The same specific treatment is required for AEPIs as well, though only to AEPIs that have been retained for further treatment consideration after identifying those that have been assessed by the investigator as possibly related to any study treatment and/or as an imAE.

Other significant adverse events (OAE)

During the evaluation of the AE data, an AstraZeneca medically qualified expert will review the list of AEs that were not reported as SAEs and 'Discontinuation of Investigational Product due to Adverse Events' (DAEs). Based on the expert's judgement, significant adverse events of particular clinical importance may, after consultation with the Global Patient Safety Physician, be considered other significant adverse events (OAEs) and reported as such in the CSR. A similar review of laboratory/vital signs/ECG data will be performed for identification of OAEs.

Examples of these are marked hematological and other laboratory abnormalities, and certain events that lead to intervention (other than those already classified as serious) or significant additional treatment.

3.4.2 Laboratory data

Laboratory data will be collected throughout the study, from screening to the follow-up visits as described in the CSP. Blood and urine samples for determination of hematology, clinical chemistry, and urinalysis will be collected as described in Section 8.2.1 of the CSP. For the definition of baseline and the derivation of post baseline visit values considering visit window and how to handle multiple records, derivation rules as described in Section 4.1.2 will be used.

Change from baseline in hematology and clinical chemistry variables will be calculated for each post-dose visit on treatment. CTCAE grades will be defined at each visit according to the CTCAE grade criteria using project ranges as required, after conversion of lab result to corresponding preferred units. The following parameters have CTCAE grades defined for both high and low values: absolute Lymphoctyes, Potassium, Sodium, Magnesium, Glucose and Corrected calcium.

Corrected Calcium will be derived during creation of the reporting database using the following formula:

Corrected calcium = Total calcium (mmol/L) + ($[40 - Albumin (G/L)] \times 0.02$)

Calculated creatinine clearance (CrCl) will be derived according to the Cockroft-Gault formula (using most recent body weight measurement if available, otherwise subsequent weight can be used) (Cockcroft and Gault 1976).

Males:

Creatinine CL =
$$\frac{\text{Weight (kg) x (140 - Age)}}{72 \text{ x serum creatinine (mg/dL)}}$$

Females:

Creatinine CL =
$$\frac{\text{Weight (kg) x (140 - Age)}}{72 \text{ x serum creatinine (mg/dL)}} \times 0.85$$

Absolute values will be compared to the project reference range and classified as low (below range), normal (within range or on limits of range) and high (above range).

The maximum or minimum on-treatment value (depending on the direction of an adverse effect) will be defined for each laboratory parameter as the maximum (or minimum) post-dose value at any time.

Local reference ranges will be used for the primary interpretation of laboratory data at the local laboratory. Project reference ranges will be used throughout for reporting purposes. The denominator used in laboratory summaries of CTCAE grades will only include evaluable patients, in other words those who had sufficient data to have the possibility of an abnormality.

For example:

- If a CTCAE criterion involves a change from baseline, evaluable patients would have both a baseline and at least 1 post-dose value recorded.
- If a CTCAE criterion does not consider changes from baseline, to be evaluable the patient needs only to have 1 post dose-value recorded.

3.4.3 ECGs

ECG data obtained up until the 30 days from date of last dose of study treatment will be used for reporting. Resting 12-lead electrocardiograms (ECGs) are recorded at screening and as clinically indicated thereafter. Categorical summaries of change from baseline in overall ECG assessments (recorded as "abnormal" and "normal") will be created if sufficient number of ECG assessments are recorded. Where triplicate values are recorded, the average will be used in summary tables, where relevant. Individual values will be reported in listing.

3.4.4 Vital signs

Vital signs data obtained up until the 30 days from date of last dose of study treatment will be used for reporting. Change from baseline in vital signs variables will be calculated for each post-dose visit on treatment. For derivation of post baseline visit values considering visit window and to handle multiple records, derivation rules as described in Section 4.1.2 will be used.

3.4.5 Treatment exposure

Exposure will be defined as follows and calculated separately for "durvalumab or placebo" and "tremelimumab or placebo". Exposure in each treatment group is the maximum of calculated values from the two components.

Total (or intended) exposure

• Total (or intended) exposure = the earliest of (date of last dose date of study drug where valid dose is considered + 27 days, death date or DCO) – first dose date + 1 day.

Actual exposure

 Actual exposure is defined as intended exposure, but excluding total duration of dose interruptions and cycle delays

Dose reductions for durvalumab, tremelimumab, or placebo are not permitted per the CSP. The actual exposure calculation makes no adjustment for any dose reductions that may have occurred.

Exposure will also be measured by the number of cycles received. If a cycle is prolonged due to toxicity, this should still be counted as one cycle. A cycle will be counted if treatment is started even if the full dose is not delivered.

Calculation of duration of dose delays (for actual exposure):

• Duration of dose delays will be calculated as follows for each dose and summed over the entire dosing period to obtain a total duration of dose delay:

If Date of the dose – Date of the previous dose \geq 31 days (28 + 3 days) then

Duration of dose delay= Date of the dose - Date of previous dose - 31 days

Otherwise duration of dose delay will be zero.

Valid dose rule

A valid dose of treatment will be classed as:

- At least one record with "DURVALUMAB/PLACEBO" or "TREMELIMUMAB/PLACEBO" and where the start date is non-missing.
- Volume of infusion must be greater than 0 (before after)
- Study Drug Dose per administration must not be 0 or missing.

Dose unit conversion

Dose of durvalumab and tremelimumab is collected in mL. To be reported in units of mg using the following conversions:

Durvalumab:

$$dose in mg = dose in mL x 50$$

e.g.
$$30mL \times 50 = 1500mg$$

Tremelimumab:

$$dose in mg = dose in mL x 19.73684211$$

e.g.
$$3.8$$
mL \times $19.73684211 = 75$ mg

Patients who permanently discontinue during a dose delay

If a decision is made to permanently discontinue study treatment in-between cycles or during a dose delay, then the date of last administration of study medication recorded will be used in the programming.

3.4.6 Dose intensity

Dose intensity will be derived for each treatment group. Relative dose intensity (RDI) is the percentage of the actual dose intensity delivered relative to the intended dose intensity through to treatment discontinuation.

RDI will be defined as follows:

• RDI = 100% * d/D, where d is the actual cumulative dose delivered up to the actual last day of dosing of the respective treatment (durvalumab or tremelimumab) and D is the intended cumulative dose up to the actual last day of dosing of the respective treatment. D is the total dose that would be delivered, if there were no modification to dose or schedule. When accounting for the calculation of intended cumulative dose 3 days may be added to the date of last dose to reflect the protocol allowed window for dosing.

• The dosing of "durvalumab or placebo" and "tremelimumab or placebo" will be considered together in the derivation, i.e. actual and intended cumulative dose in the first 4 cycles taken as the sum of doses from the two components.

When deriving actual cumulative dose administered the volume before and after infusion will also be considered.

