## 8.4.5 Management of IP-related toxicities

The following general guidance should be followed for management of toxicities.

• Treat each of the toxicities with maximum supportive care (including holding the agent suspected of causing the toxicity if required).

- If the symptoms promptly resolve with supportive care, consideration should be given to continuing the same dose of the assigned IP along with appropriate continuing supportive care. If medically appropriate, dose modifications are permitted
- All dose modifications should be documented with clear reasoning and documentation of the approach taken.

All toxicities will be graded according to NCI CTCAE, Version 4.03.

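### The single pooled RDI in SAP 3.4.6 cannot show tremelimumab delivery, because tremelimumab is only 4.76% of the summed dose

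*SAP*

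**What the plan says.** SAP Section 3.4.6 describes RDI as actual dose intensity "relative to the intended dose intensity through to treatment discontinuation", computed as 100% × d/D. Its first bullet takes d as the "actual cumulative dose delivered up to the actual last day of dosing of the respective treatment (durvalumab or tremelimumab", and gives D, the dose intended without any change to dose or schedule, the same end date. Its second bullet says that the two components are handled together, with "actual and intended cumulative dose in the first 4 cycles taken as the sum of doses from the two components".

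Section 3.4.5 collects the dose of each drug in mL and gives a separate conversion for each: "To be reported in units of mg using the following conversions". On duration, the same section says "Exposure will be defined as follows and calculated separately for" each component, but then "Exposure in each treatment group is the maximum of calculated values from the two components".

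Section 4.2.20 lists the planned output: one RDI per treatment group, plus total and actual exposure, cycles, infusions, and dose delays. It does not say that any of these are split by component.

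**The concern.** The two drugs are dosed on very different mg scales, so a sum of mg is nearly all durvalumab. A combination-arm patient can miss a quarter or half of the planned tremelimumab and still show a pooled RDI close to 100%. A reader of the exposure table would then take near-complete delivery of the regimen as near-complete delivery of both drugs.

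The tolerability of the combination is part of the safety objective, and how much tremelimumab patients could be given is one of the facts needed to judge it. What is at stake is whether that table can answer the question.

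**Working it through.** The documents state no RDI value to reproduce. The SAP's unit conversions do reproduce: 30 mL × 50 = 1500 mg, and 3.8 mL × 19.73684211 = 75.0 mg.

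**Inputs**
- Durvalumab 1500 mg every 4 weeks plus tremelimumab 75 mg every 4 weeks for up to 4 cycles, then durvalumab alone (SAP 1.2).
- Up to 26 cycles (Protocol Table 1, where C26 is the final dosing visit).
- RDI = 100 × d/D, summed over components in cycles 1 to 4 (SAP 3.4.6), in mg (SAP 3.4.5).

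**Share of the sum.** 75/(1500 + 75) = 75/1575 = 4.76%. The weight-based doses of 20 and 1 mg/kg in Protocol 6.1.2 have the same 20:1 ratio and so give the same share (1/21).

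**Planned dose.** Over 4 cycles, D = 4 × 1500 + 4 × 75 = 6300 mg. Over 26 cycles, D = 26 × 1500 + 4 × 75 = 39300 mg.

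**Patterns.** The missed dose is mid-course and not made up. Everything else is given in full and on schedule.

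| Missed | Pooled, 4 cycles | Pooled, 26 cycles | Tremelimumab alone |
|---|---|---|---|
| One tremelimumab dose | 6225/6300 = 98.8% | 39225/39300 = 99.8% | 225/300 = 75% |
| Two tremelimumab doses | 6150/6300 = 97.6% | 39150/39300 = 99.6% | 150/300 = 50% |
| One durvalumab dose | 4800/6300 = 76.2% | 37800/39300 = 96.2% | 100% |
| Both infusions of one combination cycle | 4725/6300 = 75.0% | 37725/39300 = 96.0% | 225/300 = 75% |

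**Upper bound.** With durvalumab complete, losing all four tremelimumab doses costs 300/6300 = 4.76 points over 4 cycles and 300/39300 = 0.76 points over 26.

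**Both infusions missed.** Over 4 cycles the pooled value and both component values are 75%. Over 26 cycles the pooled value follows durvalumab (25/26 = 96.2%) and no longer reflects the tremelimumab figure of 75%.

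**Permanent stop.** Suppose tremelimumab stops after dose 1 and durvalumab continues. With D ending at tremelimumab's own last dosing day, its component RDI is 75/75 = 100%. If the pooled D uses the same end date, the pooled RDI is 100% too. If the pooled D counts all four planned doses, the pooled RDI is 6075/6300 = 96.4% over 4 cycles. A component RDI therefore does not show this case; a count of doses received does.

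**Unit.** Section 3.4.6 does not name the unit of the sum. In mL the share is 3.8/33.8 = 11.2%, and one skipped tremelimumab dose over 4 cycles gives (120 + 11.4)/135.2 = 97.2%. The masking is weaker but remains.

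**The case against.** **The two bullets are compatible.** A reader might infer that Section 3.4.6 contradicts itself, because its first bullet speaks of the respective treatment and its second of a sum. The text does not force that reading. The first bullet can define d and D for each component up to its own last dose, and the second can say how to combine them. Deriving dose intensity per treatment group fits a deliberate regimen-level measure. This stands: the wording needs clarifying, but it is not a contradiction.

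**The case may be rare.** SAP 3.4.1 provides for "in the unlikely event of the two components being administered separately". Against that, Protocol 8.4.5 allows supportive care "including holding the agent suspected of causing the toxicity if required", so one component may be held while the other continues. The detailed toxicity guidelines are an annex that is not among the documents, and no frequency is given. Rarity can be neither assumed nor excluded.

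**Other tables may show it.** Section 4.2.20 includes infusions, cycles and delays, and under the Section 3.4.5 rule a skipped tremelimumab dose would count as a delay of 56 − 31 = 25 days at component level. But no split by component is stated, and an unsplit infusion count is ambiguous: 26 durvalumab plus 3 tremelimumab infusions makes 29, and so does 25 plus 4. Group exposure is the maximum over components, so the longer durvalumab course will normally set it. Table shells are not among the documents and may contain a split.

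**Total omission is handled elsewhere.** Under SAP 2.1.3, patients who receive durvalumab but never tremelimumab are summarized in the durvalumab arm, so they do not affect the combination arm's RDI. This stands.

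**Conclusion.** The point holds as a limitation of one descriptive exposure summary. Following the stated rule gives a pooled RDI of 98.8% (4 cycles) to 99.8% (26 cycles) when 75% of planned tremelimumab was delivered, and no amount of missed tremelimumab can move it by more than 4.76 points. The figures assume a sum in mg, durvalumab complete and on schedule, and a mid-course dose not made up. They show what the formula does, not how often it happens; the number of patients affected is unknown.

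Two stronger conclusions might be inferred and are not supported. The first is that the study report will hide tremelimumab delivery: the documents show only that the SAP lists no component-level RDI and states no component split, and the table shells are unseen. The second is that the combination comparison is compromised: RDI enters no test, alpha allocation, endpoint or analysis set. The change is worth making because it is cheap.

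**What to change.** In SAP 3.4.6, report RDI separately for durvalumab/placebo and tremelimumab/placebo. The pooled regimen figure may be kept as an addition. State that D runs to each component's own last dosing day, and reword the first bullet so that its relation to any pooled figure is clear.

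In SAP 4.2.20, add component-level RDI and a table of the number of tremelimumab doses received (1, 2, 3 or 4) in the combination arm. The count is needed as well as the component RDI, since only the count shows a permanent stop. With tremelimumab RDI reported separately, one skipped and resumed dose would read 75% for tremelimumab and 100% for durvalumab.

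The cost is SAP wording and a few table rows. Doses are already collected for each component and exposure is already calculated by component, so no new data are needed.
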